4.6 Safety Analyses

The domain safety covers exposure, adverse events, vital signs, ECG, and clinical laboratory.

Tables, figures, and listings are provided for SAS unless otherwise stated. All tabulations of safety data (AEs, laboratory parameters, vital signs, and ECG) will be based on both the on-treatment period and on-study period respectively unless otherwise stated.

Table 3. Overview of safety objectives

Statistical objectives	Endpoint	Population	Inter-current event strategy	Population level summary	Details in section
Primary Safety objectives					
Objective 1:					
To assess the safety and tolerability of AZD4831 as compared with placebo in participants with non-cirrhotic NASH with fibrosis.	AEs and clinical and laboratory assessments	SAS	While on treatment strategy; Treatment policy strategy	Descriptive statistics	4.6

- **Treatment** Actual treatment group (i.e., not necessarily the treatment a subject was randomized to), AZD4831 5mg or placebo administered in addition to optimal background therapy for co-morbidities
- **Population:** Safety Analysis Set
- **Endpoint:** AEs and clinical laboratory assessments
- **Intercurrent events:** Premature study treatment discontinuation: All analyses will be provided using two complementary strategies:
 - While on treatment strategy: Uses all available data collected during the on-treatment analysis period, defined in section [3.3.1.2](#)
 - Treatment policy strategy: Ignoring study treatment discontinuation, implemented by including all available data, using the on-study analysis period defined in section [3.3.1.2](#)
- **Population-level summary:** Descriptive Statistics

4.6.1 Exposure

4.6.1.1 Definitions and Derivations

Duration of exposure (days) to study drug will be calculated for each subject as

$$\text{Duration of exposure (days)} = \text{date of last dose} - \text{date of first dose} + 1$$

Dose interruptions will not be taken into consideration for calculation of duration of exposure.

Total time of exposure (subjects-years) is calculated as

$$\text{Total time of exposure} = \text{sum}(\text{duration of exposure for each subject}) \div 365.25$$

4.6.1.2 Presentation

Duration of exposure and Total time of exposure will be presented.

Total exposure will be presented categorically by cumulative categories by every 28th day from day 1 to day 85. These categories are cumulative, and subjects will be included in all categories that apply to them.

In addition, a figure of exposure over time will be presented, and percentage of subjects still exposed on the y-axis and time from first dose on the x-axis. At a given time t, the curve will show the percentage of subjects with exposure time > t.

4.6.2 Adverse Events

4.6.2.1 Definitions and Derivations

Each adverse event will be assigned to the on-treatment period and/or on-study period, as defined in Section 3.3.1.2. Adverse events will be classified by SOC and PT and coded using the most recent version of the Medical Dictionary for Regulatory Activities (MedDRA) that will have been released at the time of database lock.

Any AE

Defined as an AE reported with an onset date within the defined period.

Any SAE

Defined as an AE reported as serious irrespective of outcome.

SAEs with outcome death

Defined as an AE with reported outcome as ‘Fatal’, there may be more than one AE with outcome death for a subject. The onset date of the AE determines the analysis period, irrespective of date of death.

AEs leading to discontinuation of IP

Defined as an AE with action taken IP reported as drug permanently discontinued. The onset date of the AE determines the analysis period irrespective of date of discontinuation of IP.

AEs possibly related to IP

Defined as an AE that is reported as “reasonable possible AE caused by IP”. If this evaluation is missing, it will be counted as an AE possible related to IP.

AEs by maximum intensity

AEs will be classified by the reported maximum intensity, “Mild”, “Moderate” and “Severe”. If this maximum intensity is missing, it will be classified as “Severe”.

Adverse events of special interest

The following two groups of adverse events are Adverse events of special interest (AEoSI):

- Infections: will be identified by the SOC “Infections and infestations”.
 - The pathogen-specific High level group term (HLGT) "Fungal infections disorders".
- Skin reactions, including maculopapular rash:
 - Skin reactions/rashes considered maculopapular (described as macules/papules under the morphology/appearance question).
 - Skin reactions/rashes not considered maculopapular (not described as macules/papules under the morphology/appearance question).

4.6.2.2 Presentation

Adverse events will be presented for each treatment group by System Organ Class and/or Preferred Term covering number and percentage of participants reporting at least one event and number of events where appropriate.

An overview AE table will be presented for each treatment group including number and percentage of participants with any AE, AEs with outcome of death, serious AEs, and AEs leading to discontinuation of IP.

Separate AE tables will be provided taking into consideration seriousness, death, and events leading to discontinuation of IP. An additional table will present number and percentage of participants with most common AEs, where most common is defined as more than 5% per treatment group.

In accordance with the requirements of the FDA, a separate table will present nonserious AEs occurring in more than 5% of participants in any treatment group. Key participant information will be presented for participants with AEs with outcome of death, serious AEs, and AEs leading to discontinuation of IP. An AE listing for the safety analysis set will cover details for each individual AE. Adverse events of special interest related to skin reactions, including maculopapular rash, and infection will be presented.

For the summary of AEs by PT and maximum intensity, if a patient has multiple events occurring in same PT within a treatment phase, then the event with the highest intensity will be counted. For the summary of AEs by PT and investigator's causality assessment, if a patient has multiple events occurring in same PT within a treatment phase, then the event with the maximum reported causality will be counted.

4.6.3 Clinical Laboratory, Blood Sample

4.6.3.1 Definitions and Derivations

Blood samples for determination of clinical chemistry and haematology will be collected according to the schedule of activities in Section 1.3 of the CSP. Clinical Safety Laboratory Assessments are listed in Section 8.2.5 of the CSP.

4.6.3.2 Presentations

Clinical laboratory parameters will be presented for SAS by treatment group, and scheduled visit, separately for haematology and chemistry parameters, and the parameters will be presented in alphabetical order.

Values and absolute change from baseline will be presented for continuous variables using descriptive statistics for all scheduled assessments after baseline.

Maximum on-treatment/on-study ALT and AST versus maximum on-treatment/on-study total bilirubin will be presented by treatment group.

Shift tables will be presented for all subjects by treatment.

4.6.4 Clinical Laboratory, Urinalysis

4.6.4.1 Definitions and Derivations

Clinical laboratory parameters for urinalysis will be presented for SAS by treatment group, and the parameters will be presented in alphabetical order.

Change from baseline to maximum and minimum assessment on-treatment and on-study respectively will be presented in shift tables.

Urinalysis will be taken according to the schedule of activities in section 1.3 in the CSP.

4.6.4.2 Presentation

Clinical laboratory parameters for urinalysis will be presented for the safety analysis set by the treatment group and scheduled visit. All parameters will be presented with descriptive statistics for all visits for which an assessment is scheduled.

4.6.5 Other Laboratory Evaluations

Not Applicable.

4.6.6 Vital Signs

4.6.6.1 Definitions and Derivations

Vital signs (supine BP [average of 3 measurements], pulse rate, height, weight, and body temperature) will be performed at the time points specified in the Schedule of Assessments in the CSP.

4.6.6.2 Presentations

Vital sign parameters will be presented for each treatment group. Summary statistics for continuous variables cover n, mean, SD, min, Q1, median, Q3, and max. For each scheduled post-baseline visit, descriptive statistics for all vital sign parameters will be presented for observed values and change from baseline.

Listings

Listings of vital signs will be presented for all patients

4.6.7 Electrocardiogram

4.6.7.1 Definitions and Derivations

Electrocardiograms will be performed and measured as specified in the CSP.

ECG treatment emergent changes are defined as subjects with abnormal clinically significant results on-treatment that were not present at baseline.

4.6.7.2 Presentations

Summary statistics will be shown for the following categories for the Safety Analysis Set by treatment group:

- Heart rhythm category
- Overall ECG evaluation
- Was the ECG clinically significant?

Shifts from baseline to last observation on-treatment in ECG overall evaluation will be analyzed in terms of normality and clinical significance.

Treatment emergent changes

The number and percentage of subjects with ECG treatment emergent changes will be presented by treatment group for SAS, where the percentage is based on number of subjects per treatment group with a baseline value and at least one post-baseline value on treatment.

Listings

A listing for all subjects will present date of ECG performance, categories listed above and reasons if conduction was abnormal.

Electrocardiogram evaluation will be summarized and presented by treatment group for baseline and for each scheduled post-baseline assessment.

4.6.8 Other Safety Assessments

4.6.8.1 Definitions and Derivations

Orthostatic blood pressure test

Orthostatic hypotension related measures are derived from the orthostatic BP measurements. The orthostatic hypotension test is described in Section 8.2.3.1 in the CSP. The following definitions will be applied:

- BP decrease: a decrease ≥ 20 mmHg in systolic blood pressure or ≥ 10 mmHg in diastolic blood pressure.
- BP decrease reported as AE: a BP decrease and a reported AE of Orthostatic Hypotension the same day post-first dose or within the same day of the at 12 weeks measurement.
- Symptomatic BP decrease: BP decrease which the investigator judges that there were symptoms that were related to the orthostatic blood pressure measurement.
- Asymptomatic BP decrease: BP decrease which the investigator judges that there were no symptoms that were related to the orthostatic blood pressure measurement.

These categories will be presented at three timepoints:

- Post-first dose irrespective of baseline status,
- only post-first dose (including only subjects with no observed BP decrease pre-first dose), and
- at 12 weeks.

Orthostatic hypotension visit window

The orthostatic hypotension analysis visit window is calculated based on first-dose date. The visit windows are the same days from baseline (, first-dose date for orthostatic hypotension,) as for other assessments.

4.6.8.2 Presentations

Orthostatic blood pressure test

Measurements related to the Orthostatic hypotension test will be summarized for each of the three timepoints described in Section 4.6.8.1 by number and percentage of subjects with an event and total number of events based on the safety analysis set, by treatment group.

The tables will display data for two groups: the full analysis set and the subgroup with stable supine measurements.

If replicate measurements differ by no more than 10 mmHg for systolic and 5 mmHg diastolic, respectively, the supine BP will be considered stable.

Listings

A listing of all orthostatic test results will be provided.

A listing of AEs, SAEs and DAEs by SOC/PT for subjects with at least one test sequence suggestive of Orthostatic hypotension will be presented. Adverse events occurring within 3 hours after first dose of IP for the baseline visit or the 12 weeks measurement will be flagged.

5 INTERIM ANALYSIS

Not Applicable.

7 APPENDIX

7.1 Baseline definitions

If there are multiple measurement on the same date, the algorithm below decides which measurement to use as baseline.

For analyses on the safety analysis set (SAS), baseline is determined as follows:

- If there is at least one non-missing value collected on the date of first dose and prior to the time of first dose, then baseline is defined as the last non-missing value prior to the time of first dose on the date of first dose.
- Else if there is at least one non-missing value collected on the date of first dose and with missing time, then baseline is defined as the non-missing value with missing time on the date of first dose.
- Else if the only values collected on the date of first dose are on or after the time of first dose, then baseline is defined as the first non-missing value on or after the time of first dose on the date of first dose.

- Else if there are no non-missing values collected on the date of first dose, then baseline is defined as the last non-missing value prior to the date of first dose.

Note: if multiple non-missing values collected on the same date qualify for baseline and include both records with missing time and records with non-missing time, then the records with missing time will not be considered as eligible to be used as baseline.

If after performing the above steps there are still multiple non-missing values equally eligible to be used as baseline, then baseline is defined as an average of the tied quantitative values or as the clinically best value among the tied qualitative values.

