#### **9.4.1 General Considerations**

All personnel involved with the analysis of the study will remain blinded until database lock and protocol violations have been identified and documented. Analyses will be performed by AstraZeneca or its representatives.

Nominal significance will be 5% and all tests will be one-sided. All confidence intervals will be 2-sided and 95%.

No multiplicity adjustment for alpha is planned.

For analyses both on the FAS and on the SAS, baseline is defined as the last non-missing value prior to first dose including unscheduled assessments that occurs prior to first dose.

All summary statistics will be presented in total, divided by fibrosis stage, and divided by T2DM status.

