2 CHANGES TO PROTOCOL PLANNED ANALYSES

Full analysis set have been changed to include patients who are randomized and have been given at least one dose.

Analysis on explorative endpoint *Oxidative damage biomarkers* are not included in CSR.

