3.3 General Considerations

3.3.1 General Study Level Definitions

3.3.1.1 Baseline

For Safety Analysis Set (SAS), baseline is last non-missing value prior to or on first dose date, for further details see appendix.

For analyses on the full analysis set (FAS), baseline is determined according to the same rules as for analyses on SAS, except that for subjects whose date of first dose is different from the date of randomization baseline is determined as follows:

- Baseline is defined as the last non-missing value prior to or on the date of randomization.

For both FAS & SAS, post-baseline is defined as any value after baseline value.

Further details on selecting which measurement to use as baseline value are explained in Appendix [7.1](#).

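### SAP 7.1 lets a Day 1 value taken at or after first dose become baseline ahead of a known pre-dose value, contrary to Protocol 9.4.1 and undeclared

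*SAP*

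**What the plan says.** Protocol 9.4.1 sets one rule for the FAS and the safety analysis set: "baseline is defined as the last non-missing value prior to first dose including unscheduled assessments that occurs prior to first dose".

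SAP 7.1 replaces this with four ordered steps for the safety analysis set:

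1. Take the last timed value on the day of first dose that precedes the dose.
2. Otherwise take an untimed value from that day. The condition reads "Else if there is at least one non-missing value collected on the date of first dose and with missing time".
3. Otherwise, if the only values that day are at or after dosing, "then baseline is defined as the first non-missing value on or after the time of first dose on the date of first dose".
4. Only then take a value from an earlier date. The condition reads "Else if there are no non-missing values collected on the date of first dose".

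The summary in SAP 3.3.1.1 is worded by day rather than by dose: "baseline is last non-missing value prior to or on first dose date". For the FAS it adds that "baseline is determined according to the same rules as for analyses on SAS", with one exception for participants first dosed on a day other than the day of randomization.

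SAP Section 2 lists two changes from the protocol. One is that "Full analysis set have been changed to include patients who are randomized and have been given at least one dose"; the other drops an exploratory biomarker analysis. Baseline is not listed. The SAP amendment history records the new baseline algorithm as consistent with the protocol and as a clarification.

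**The concern.** Baseline should be free of treatment. Step 3 breaks that in the one situation it covers: it prefers a value taken after exposure to a known value taken before it. In the active arm, any early drug effect would then sit in the reference value as well as in the follow-up value.

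The reach is formally wide. Because SAP 3.3.1.1 sends the FAS to the same rules, they fix the baseline for ALT, where baseline is both part of the endpoint and the model covariate (Protocol 9.4.2.1). They also fix it for Pro-C3, safety laboratory values and vital signs.

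The missing declaration matters separately. For the FAS change, the sponsor entered a departure from the protocol in the amendment history, with a reason, and repeated it in Section 2. By that standard the baseline change belongs there too. A reader relying on Section 2 would assume that the protocol's baseline still applies.

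**Working it through.** **The two rules applied to the same records**

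| Records available | SAP 7.1 | Protocol 9.4.1 |
|---|---|---|
| Earlier value and timed pre-dose Day 1 value | Day 1 pre-dose (step 1) | Day 1 pre-dose |
| Earlier value and untimed Day 1 value | untimed Day 1 value (step 2) | the same if it was pre-dose; otherwise the earlier value |
| Earlier value and post-dose Day 1 value only | post-dose value (step 3) | earlier value |
| Earlier value only | earlier value (step 4) | earlier value |
| Post-dose Day 1 value only | post-dose value (step 3) | missing |

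The rules conflict outright in rows 3 and 5. Row 3 can arise for ALT, because inclusion criterion 4 requires a screening ALT. Row 5 could arise for Pro-C3 if no screening sample exists; Table 2 as extracted appears to show none, but its columns are broken.

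The FAS exception in SAP 3.3.1.1 also differs from 9.4.1. It still yields a pre-dose value when dosing falls on a later day, so it is a consistency point only.

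**How often step 3 could be triggered.** Table 2 footnotes place the blood draws pre-dose and study drug after PK sampling. Protocol 8.2.3 places vital signs before blood sampling. Step 3 therefore needs a missing or mistimed pre-dose value. The documents give no count.

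**The plan's own figures.** Inputs from Protocol 9.2 and SAP 1.3: 25% decrease, so τ = ln 0.75 = −0.2877; SD 0.50; one-sided 5%; 80% power. Then n = 2 × (1.645 + 0.842)² × 0.50² / 0.2877² = 37.4, or 38 per arm. At the SAP's 40 per arm, power is 81.7% (t-test), and 40/0.9 = 44.4, or 45. The plan's figures reproduce. Only the 25% and the 45 are used below.

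**Effect of step 3 on the ALT contrast.** The baseline-adjusted contrast is (Y1 − Y0) − b(B1 − B0). Suppose k of 45 active baselines are post-dose, each shifted by fτ. The contrast is then attenuated by the fraction b·f·k/45, and the decrease shown is 1 − exp[τ(1 − b·f·k/45)].

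Assumptions: b is the slope of follow-up on baseline; f is the share of the Week 12 effect present within hours of one tablet. Neither b, f nor k is in the documents.

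| b | f | k | Attenuation | 25% decrease shows as |
|---|---|---|---|---|
| 0.5 | 0.1 | 1 | 0.11% | 24.98% |
| 0.5 | 0.1 | 3 | 0.33% | 24.93% |
| 0.5 | 0.1 | 5 | 0.56% | 24.88% |
| 0.3 | 0.05 | 5 | 0.17% | 24.96% |
| 0.8 | 0.2 | 5 | 1.78% | 24.62% |

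A simulation (45 per arm, ANCOVA on log ALT, b = 0.5, k = 5, 6,000 runs) gave 0.278%, 0.551% and 1.112% for f = 0.05, 0.1 and 0.2, against 0.278%, 0.556% and 1.111% from the formula.

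**Error of the fallback.** A screening ALT has been selected for exceeding the ULN, so it tends to overstate the Day 1 level. Assumptions: geometric mean ALT 1.3 to 2.0 × ULN; between-person log SD 0.35 to 0.45; within-person log SD 0.20 to 0.354 (0.354 = 0.50/√2); selection on historical and screening ALT above ULN, with screening ALT at most 5 × ULN. The mean excess is then 0.3% to 9.8%, in either arm. It cancels if both arms use the fallback equally. With an excess of 0.10 log, b = 0.5 and an imbalance of two participants, the contrast moves by 0.5 × 0.10 × 2/45 = 0.0022 log, so a 25% decrease shows as 24.83% or 25.17%.

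**The case against.** The strongest reply is that nothing material follows. The number affected may be zero, sampling is planned pre-dose, and the ALT effect is tiny on any of the assumed inputs. That stands, and it is why the point is of low severity.

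It can also be said that the remedy may be less accurate for an affected individual. At f = 0.1, step 3 shifts an active participant's ALT by 0.1 × (−0.2877) = −0.0288 log, about −2.8%, and leaves a placebo participant's unchanged. The fallback may be off by more. This also stands, as a cost. But the fallback's error does not depend on treatment, whereas step 3's error arises only under active drug, and the protocol has already made the choice.

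Two stronger readings are tempting and are not supported:

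- **That step 2 also contradicts the protocol.** An untimed Day 1 value is pre-dose by plan, so accepting it is a reasonable way to apply the protocol's rule.
- **That a post-dose reading is lost from the safety follow-up**, because "post-baseline is defined as any value after baseline value". This is largely empty. The first post-baseline visit window opens on Day 12 (SAP 3.3.2), so no Day 1 reading enters a by-visit post-baseline summary under either rule. The on-treatment and on-study periods start on the date of first dose (SAP 3.3.1.2), so on their face the displays of maximum ALT and AST against bilirubin still include it.

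**Conclusion.** The contradiction holds on the text. SAP 7.1 step 3, with the restrictive condition on step 4, allows a baseline that Protocol 9.4.1 does not. SAP 3.3.1.1 repeats the conflict and extends it to every FAS and safety baseline. Section 2 does not declare it.

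A reader might infer that the primary ALT result is at risk. The documents do not support that: expected frequency is low, and with five affected active participants the attenuation is about 0.2% to 1.8% under assumed b and f. A reader might equally infer that only safety data are touched. SAP 3.3.1.1 rules that out. The case rests on an undeclared contradiction and on a treatment-exposed reference value for any participant in whom step 3 is triggered.

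Two limits apply. The text of SAP 4.2.1 was removed from the copy reviewed, so a separate ALT baseline rule cannot be excluded. The SAP also serves three regional protocols, and only the one dated 20 March 2023 was available. Severity: low.

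**What to change.** In SAP 7.1, delete step 3 and reword step 4 along these lines: *Else, if no eligible pre-dose value exists on the date of first dose, take the most recent non-missing value from an earlier date.* Step 2 may stay. In SAP 3.3.1.1, replace the day-level wording with *prior to first dose*.

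If no pre-dose value exists at all, treat baseline as missing and, for ALT and Pro-C3, impute it. One further mismatch then needs attention: SAP 7.2 imputes a missing baseline with the mean of the observed baselines, while Protocol 9.4.2.1 specifies PROC MI MCMC. That should be reconciled or declared as well.

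The cost is one deleted step, two wording changes and an update to the derivation code. The downside is that a few baselines would come from a screening value up to 8 weeks old. For laboratory values this may be Visit 1, since Visit 3 safety laboratory tests are required only of participants needing a fresh biopsy (Table 2 footnote k, text in the amendment summary). For ALT such a value is prone to regression to the mean, in either arm.

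If the sponsor prefers to keep step 3, it should declare it in SAP Section 2 with the reason and correct the amendment-history entry to show that it departs from the protocol.
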